5.6. Treatment Misallocations

If a subject takes a treatment that is not consistent with the treatment they are randomized to, then they will be reported under their randomized treatment group for efficacy analyses, but will be reported under treatment they actually received for all other analyses.

5.7. Protocol Deviations

Different protocol deviations may have different impact on the analyses. A full list of protocol deviations will be compiled and reviewed prior to database closure. In protocol deviation review meetings, the classification of major and minor protocol deviations will be carried out by the clinician and statistician prior to unblinding and a decision will be made for each subject's eligibility for PPS analysis set.

5.7.1. Deviations Assessed Prior to Randomization

At screening, the investigator will assess subjects against the inclusion and exclusion criteria as set out in Sections 4.1 and 4.2 of the protocol.

5.7.2. Deviations Assessed Post-Randomization

Any significant deviation from the protocol will be reviewed prior to database closure and a decision taken regarding evaluation for each analysis population.

6. ENDPOINTS AND COVARIATES

6.1. Efficacy Endpoint(s)

6.1.1. Primary Efficacy Endpoint

- *Change relative to baseline at Day 19 in psoriatic skin infiltrate thickness/EPB.*

6.1.2. Secondary Efficacy Endpoint

- *AUC of the psoriatic skin psoriatic thickness/EPB from Day 1 to Day 19.*
- *Change relative to baseline in psoriatic skin infiltrate thickness/EPB at visit other than Day 19.*

CCI

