1.2.5. Betamethasone Solution

PF-06763809's anti-psoriatic activity will be benchmarked against that of betamethasone solution. In a similar designed study, Betnesol[®] solution reduced the skin inflammatory infiltrate by 79% relative to vehicle (data on file; bioskin[®]).

While betamethasone solution is approved for scalp psoriasis, the proposed use being highly limited on other skin surfaces in this study, does not significantly increase the risks (or decrease acceptability of risks) associated with the use of this product. As noted earlier, the SRSD is the approved product label.

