1.3.1. Design Rationale

1.3.1.1. Rationale for Design

[figure not shown]
The psoriasis plaque test (PPT) is a commonly employed methodology in the early assessment of topical agents for the treatment of psoriasis. Indeed, the skin infiltrate thickness/EPB thickness is considered an important indicator of disease activity in psoriasis and has been shown to correspond with increased inflammatory cell infiltrates, capillary congestion, and/or edema in the superficial dermis as identified by histopathology.^{24,25} Given that the extent of the psoriatic infiltrate is an important clinical endpoint in psoriasis, the PPT relies on an objective biophysical measurement of psoriatic skin infiltrate thickness/EPB

CCI

to support traditional clinical endpoints in psoriasis.

[figure not shown]
Testing is conducted under optimized conditions using small skin surface areas located on stable psoriatic plaques in subjects with plaque psoriasis. The reduction in psoriatic skin infiltrate thickness/EPB in response to PF-06763809 solution (2.3%, 0.8%, and 0.23%), when applied topically at 180 μ L to 1.1 cm^2 skin surface areas (a volume of 180 μ L applied to a 1.1 cm^2 surface, equivalent to 164 μ L/ cm^2), will be measured in subjects with stable chronic plaque psoriasis. At the end of study treatment, the change relative to baseline in psoriatic skin infiltrate thickness of treated areas with PF-06763809's will be compared with vehicle as well as two active controls, calcipotriene/calcipotriol solution (50 μ g/mL) and betamethasone (1 mg/g). The treated areas will be clinically assessed throughout the study. The study will also assess the safety and tolerability of topically applied PF-06763809 solution (2.3%, 0.8%, and 0.23%) in subjects with stable chronic plaque psoriasis.

CCI

This first-in-human study will enroll subjects with psoriasis and body mass index (BMI) of ≥ 17.5 and ≤ 35.5 kg/m^2 . Use of this increased BMI range is justified to balance the need for an otherwise healthy subject population in this first study with PF-06763809 and permit recruitment of subjects with psoriasis who have higher prevalence for obesity.²⁶

[figure not shown]
[figure not shown]
CCI

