2. STUDY OBJECTIVES AND ENDPOINTS

Primary Objective(s):	Primary Endpoint(s):

 To assess the changes in psoriatic skin infiltrate thickness/EPB in response to PF-06763809 2.3%, 0.8% and 0.23% applied topically for 18 consecutive days as compared to the vehicle control. 	
 Change relative to baseline at Day 19 in psoriatic skin infiltrate thickness/EPB.

 To determine the safety and tolerability of multiple dose topical administration of PF-06763809 in psoriasis subjects. 	
 Assessment of adverse events (AEs), clinical laboratory tests, vital signs (including blood pressure and pulse rate), and cardiac conduction intervals as assessed via 12-lead electrocardiogram (ECG).
Secondary Objective(s):	Secondary Endpoint(s):

 To evaluate the Area Under the Curve (AUC) of psoriatic skin infiltrate thickness/EPB for PF-06763809 compared to vehicle . 	
 AUC of the psoriatic skin infiltrate thickness/EPB from Day 1 to Day 19.

 To assess the effect of PF-06763809 compared to calcipotriene/calcipotriol solution in the change of psoriatic skin infiltrate thickness/EPB both within and following 18 days of treatment. 	
 Change relative to baseline in psoriatic skin infiltrate thickness/EPB.

 To assess the effect of PF-06763809 compared to betamethasone solution in the change of psoriatic skin infiltrate thickness/EPB both within and following 18 days of treatment. 	
 Change relative to baseline in psoriatic skin infiltrate thickness/EPB.
CCI 	
	
	
	
	

CCI [REDACTED]

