6.3. Follow-up

6.3.1. Follow-up Visit

In this study, there are two Follow-up visits, as follows:

1st is an **on-site visit** where only subjects who have consented to the optional biopsy or who have an open AE following completion of Day 19 will return to the CRU on Day 27 (**8 ±2 days** following Day 19);

2nd is a **telephone contact** to occur for all subjects who participated in the study, on Day 49 (**31 ± 3 days** following the last dose of investigational product);

Refer to Schedule of Activities—[Table 1](#) for the study procedures to be completed at each of the two Follow-up visits.

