2.2.2. Secondary Objectives

- *To evaluate the Area Under the Curve (AUC) of psoriatic skin infiltrate thickness/EPB for PF-06763809 compared to vehicle.*
- *To assess the effect of PF-06763809 compared to calcipotriene/calcipotriol solution in the change of psoriatic skin infiltrate thickness/EPB both within and following 18 days of treatment.*
- *To assess the effect of PF-06763809 compared to betamethasone solution in the change of psoriatic skin infiltrate thickness/EPB both within and following 18 days of treatment.*

CCI

- 
- 
- 
- 
- 

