4. HYPOTHESES AND DECISION RULES

4.1. Statistical Hypotheses

This study is designed to show that PF-06763809 has a superior effect against vehicle in the primary endpoint of relative change from baseline in infiltrate thickness at Day 19. The following hypotheses will be formally tested first under a significance level of 5% (two-sided):

- The null hypothesis (H_{01}): PF-06763809 has no greater reduction from baseline in infiltrate thickness at Day 19 than vehicle.
- The alternative hypothesis (H_{11}) is that PF-06763809 has a greater reduction from baseline in infiltrate thickness at Day 19 than vehicle.

If the null hypothesis H_{01} is rejected statistically, then the following hypotheses will be formally tested next under a significance level of 5% (two-sided):

[figure not shown]
- The null hypothesis (H_{02}): PF-06763809 has no greater reduction from baseline in infiltrate thickness at Day 19 than calcipotriene/calcipotriol.
- The alternative hypothesis (H_{12}) is that PF-06763809 has a greater reduction from baseline in infiltrate thickness at Day 19 than calcipotriene/calcipotriol.

[figure not shown]
Data from three psoriasis plaque test (PPT) studies conducted at bioskin® GmbH were used to generate the assumption for sample size calculation. In these three studies, the calcipotriene/calcipotriol solution demonstrated 36% - 44% reduction in infiltrate thickness relative to vehicle. The observed within-subject standard deviation (SD) estimates for calcipotriene/calcipotriol solution relative to vehicle ranged from 0.331-0.435. Power analyses were performed for samples sizes of N=15 and N=20 under within-subject SDs of 0.38, 0.435 and 0.5 with 2-sided type-I error rate of 5% and results were summarized C

CCI

I.

CCI

CC1

A large blacked-out rectangular area representing a redacted section of the document, likely containing sensitive information.

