8.1. Analysis of Primary Efficacy Endpoint

The primary endpoint for this study is the change relative to baseline in psoriatic skin infiltrate thickness/EPB at Day 19 [REDACTED] for PF-06763809 in comparison to vehicle. The efficacy assessment of PF-06763809 will be performed for the change from baseline in log of the psoriatic skin infiltrate thickness/EPB on Day 19 using a longitudinal analysis of covariance model, with treatment, visit, treatment by visit interaction as main effects and the log of the psoriatic skin infiltrate thickness/EPB at baseline as covariate. The CS@UN covariance structure will be assumed to adequately model the two within-subject factors (treatment, visit), where the compound symmetric (CS) correlation is for repeated measures from different treatments within each visit and the unstructured (UN) correlation is for longitudinal measures from different visits. If there are convergence issues, alternative covariance structure will be examined and adopted. The point estimate and 95% confidence interval (CI) for the difference in log transformed means at Day 19 visit between treatment groups will be constructed using least square means and appropriate standard errors. The assessment of the primary endpoint will be performed at a two-sided significance level of 0.05.

In addition, a landmark analysis of covariance (ANCOVA) model analysis of the primary endpoint at Day 19 will be performed to examine the robustness of the conclusion drawn from the primary longitudinal analyses. The landmark ANCOVA model will include treatment as the main effect, log-transformed psoriatic skin infiltrate thickness/EPB at baseline as covariate and a random subject effect to account for correlation among repeated measures from different treatments for each subject.

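### Does limiting the SAP's secondary change endpoint to visits other than Day 19 leave the Day 19 comparison with betamethasone without a place in the plan?

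*SAP*

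**What the plan says.** Both documents set secondary objectives comparing PF-06763809 with calcipotriene/calcipotriol and with betamethasone. The betamethasone objective in SAP 2.2.2 covers the effect "compared to betamethasone solution in the change of psoriatic skin infiltrate thickness/EPB both within and following 18 days of treatment". Protocol section 2 pairs these objectives with an endpoint that has no visit limit: "Change relative to baseline in psoriatic skin infiltrate thickness/EPB". SAP 6.1.2 narrows it to "Change relative to baseline in psoriatic skin infiltrate thickness/EPB at visit other than Day 19".

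Day 19 appears elsewhere in the SAP:

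- Section 6.1.1 lists Day 19 change as the primary efficacy endpoint and names no comparator.
- Section 4.1 tests superiority to vehicle first. If that succeeds, it tests whether "PF-06763809 has a greater reduction from baseline in infiltrate thickness at Day 19 than calcipotriene/calcipotriol".
- Sections 4.2 and 8.1 describe the primary endpoint as Day 19 change "for PF-06763809 in comparison to vehicle". They then call for Day 19 estimates and 95% confidence intervals for treatment differences, without limiting these to vehicle.

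The protocol also gives the active controls a purpose. Section 1.3.1.1 says end-of-treatment change "will be compared with vehicle as well as two active controls", and section 1.2.5 says the product's "anti-psoriatic activity will be benchmarked against that of betamethasone solution".

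**The concern.** Dosing runs from Day 1 to Day 18 (Protocol 5.5), so Day 19 is the natural visit for the part of the objective that follows treatment. Afterwards the protocol has an on-site visit on Day 27, "where only subjects who have consented to the optional biopsy or who have an open AE following completion of Day 19" return, and a telephone contact on Day 49. Read literally, SAP 6.1.2 removes from the secondary list the one post-treatment visit that every subject attends.

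For vehicle this does no harm, because Day 19 is primary. For calcipotriol it does little, because the second hypothesis in SAP 4.1 is set at Day 19. Betamethasone at Day 19 seems to fall between the lists: it is not in 6.1.2, not in the hypotheses, and not in the vehicle-specific description of the primary endpoint.

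The risk would be one of reporting. Betamethasone is the stronger control on the planning figures, so this is the contrast most likely to look poor for PF-06763809. A result whose status is settled only after unblinding could be given less prominence than it was meant to have.

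**Working it through.** The documents state no figure that depends on this wording, so the check is mainly a comparison of text, followed by one calculation.

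**1. What each place covers**

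| Place | Visit | Comparator |
|---|---|---|
| Protocol 2, secondary change endpoint | no limit | calcipotriol and betamethasone, through the paired objectives |
| SAP 2.2.2, objectives | during and after the 18 days | calcipotriol, betamethasone |
| SAP 6.1.1 | Day 19 | none named |
| SAP 6.1.2 | all except Day 19 | none named |
| SAP 4.1, hypotheses | Day 19 | vehicle, then calcipotriol |
| SAP 4.2 and 8.1, primary endpoint | Day 19 | vehicle |
| SAP 4.2 and 8.1, estimates and intervals | Day 19 | any treatments |

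Sections 6.1.1 and 6.1.2 list a variable by visit, and neither names a comparator. Side by side they cover every visit once. The simplest reading of the exclusion is that it avoids listing the Day 19 variable twice. The comparators come from the objectives, where betamethasone is named.

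**2. What the analysis produces**

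The SAP 8.1 model includes treatment, visit and their interaction for all six treatments. At Day 19 it gives six least-squares means, hence 6 × 5 / 2 = 15 pairwise contrasts. Three of these are the PF-06763809 strengths against betamethasone. SAP section 8 also summarises every endpoint by time point and treatment. Nothing further has to be collected or fitted.

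**3. Whether any number turns on the wording**

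Inputs: calcipotriol 38% reduction against vehicle with within-subject SD 0.435 (Protocol 1.2.4), or 36% to 44% with SD 0.331 to 0.435 across three studies (Protocol 9.1); betamethasone 79% (Protocol 1.2.5); planning SD up to 0.5 and 15 completers (Protocol 9.1). No SD is given for betamethasone, so the same SDs are assumed. Both reductions are treated as ratios to a common vehicle thickness.

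- If PF-06763809 equalled calcipotriol, the ratio to betamethasone would be (1 − 0.38)/(1 − 0.79) = 0.62/0.21 = 2.95.
- The log-scale half-width is t × SD of difference / √15, with t = 2.145 on 14 df.
- With 0.435 as the SD per field: 2.145 × 0.435 × √2 / √15 = 0.341, a factor of 1.41 and an interval of 2.10 to 4.15.
- With 0.435 as the SD of the difference: 2.145 × 0.435 / √15 = 0.241, a factor of 1.27 and an interval of 2.32 to 3.76.
- Over reductions of 36% to 44%, the ratio runs from 0.56/0.21 = 2.67 to 0.64/0.21 = 3.05. Letting the SD also run from 0.331 to 0.5 under both readings, the lower limit runs from about 1.80 to 2.54.

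These figures show that the contrast could be clear-cut. None of the inputs comes from SAP 6.1.2, so changing its wording leaves every line above as it stands.

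**The case for a change.** The strongest case for a change is that sections 4.2 and 8.1 define the primary endpoint against vehicle. Carry that definition back into 6.1.1 and the Day 19 comparisons with the actives sit in neither endpoint list, while the SAP repeats its objectives unaltered. That would be an inconsistency within the SAP. Protocol section 9 allows the SAP to depart from the protocol, but this does not explain a narrowing that the SAP never presents as deliberate. Rewording one line would cost almost nothing.

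Part of this stands. Section 6.1.2 is narrower than the objectives it serves and than the protocol's endpoint, and the SAP's own label for betamethasone at Day 19 is unclear in the readable text.

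The consequence does not stand. The gap opens only if a comparator is read into 6.1.1, which names none. Even then, the protocol's unrestricted secondary endpoint and the objective in both documents classify the comparison as secondary. SAP 2.1 also says the effect will be assessed against vehicle and both actives. What betamethasone lacks is a visible formal hypothesis, and a secondary comparison reported as an estimate with an interval does not need one.

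**Conclusion.** No change follows. This is a drafting mismatch that an analyst would resolve in the obvious way: report Day 19 change against betamethasone as a secondary comparison, with estimate and 95% confidence interval, from the model already specified. The effect on sample size, alpha, power and the primary test is nil, and the contrast has the same value under either wording.

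The conclusion rests on the readable text. The thickness measurement days, the text after SAP 6.1.2 and part of SAP 4.1 are blacked out. A hidden line might settle the label outright. The conclusion also assumes that the Day 19 contrasts for all treatments are reported, as SAP 8.1 provides and the objectives require.

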6.2. Safety Endpoints

Safety endpoints of this study include adverse events (AEs), clinical laboratory tests, vital signs (including blood pressure and pulse rate), and cardiac conduction intervals as assessed via 12-lead electrocardiogram (ECG). These safety data will be analyzed in standard safety summaries.

CCI

C

C

I

I

6.4. Covariates

Baseline values of psoriatic skin infiltrate thickness/EPB will be included as a covariate in the longitudinal and landmark analysis of covariance (ANCOVA) analysis of the primary endpoint.

7. HANDLING OF MISSING VALUES

In this primary longitudinal ANCOVA analysis of psoriatic skin infiltrate thickness/EPB, the missing data will be assumed as missing at random and no imputation will be made for missing data. In the landmark ANCOVA analysis the missing assessment of psoriatic skin infiltrate thickness/EPB will be imputed using the last observation carried forward (LOCF) procedure. *In case of treatment discontinuation the last assessment prior to treatment discontinuation will be imputed for the following planned assessment of psoriatic skin infiltrate thickness/EPB.*

Any data displays using last observation carried forward will be labeled 'LOCF'. For other data displays LOCF will not be used and subjects with missing values of a particular endpoint will not contribute to the analysis.

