1.2.3. Summary of Toxicology Studies

In nonclinical safety studies with PF-06763809 in rats (oral) and mini-pigs (dermal) of up to 1-month in duration, the cardiovascular and immune systems have been identified as potential key systemic targets and vehicle-related mild to moderate skin irritation by the topical route of administration. The no observed adverse effect levels (NOAELs) in the pivotal toxicity studies were 200 mg/kg in rats (C_{max}, 6280 ng/mL and AUC₂₄, 71,000 ng·h/mL) and the maximum feasible dose, 2.3% formulation applied at 0.02 mL/cm²/dose to ~10% body surface area, twice daily (BID), in minipigs (C_{max}, 41.3 ng/mL and AUC₂₄, 309 ng·h/mL). PF-06763809 was not identified with mutagenic or clastogenic potential from in vitro and in vivo studies. PF-06763809 did not demonstrate phototoxicity potential and did not demonstrate a sensitization potential in the in vitro sensitivity assays. Details of the nonclinical safety program are provided in the current Investigator's Brochure.

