Approximately 180 μL of each liquid preparation and 180 μL of each comparator will be applied CCI [REDACTED] under Duhring[®] chambers (12 mm inside diameter, 14 mm outside diameter) seated in holes punched in hydrocolloid dressing (eg, Varihesive[®], Bristol-Myers Squibb Gruppe, Munich, Germany). The fields will be treated under occlusion for 18 days. Subjects will return daily to the center for re-application of the test substances daily during the 18-day treatment period. Before each new application any remaining residue of the previously applied preparation will be removed gently by cleansing each test field with a clean soft tissue. Following this regimen, each preparation will be left in contact with lesional skin under a Duhring[®] chamber until removal for inspection at the next visit. This ensures that there is exposure to each preparation almost continually for the 18 days of the treatment phase of the study.

CCI

Safety will be assessed by monitoring of vital signs, safety laboratory tests (see [Section 7.1.4](#) and [7.1.1](#) respectively) and by recording of adverse events (AEs) and serious adverse events (SAEs) (see [Section 8](#)). Special attention will be given to local safety (ie, signs of skin irritation at the application sites). Skin reactions will be recorded as AEs.

The overall study design is summarized in Figure 1.

Figure 1. Overall Study Design

In this study, subjects who prematurely discontinue for non-safety related reasons may be replaced, at the discretion of the Sponsor. Up to 5 subjects may be replaced.

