3.2. Stopping Rules for Dosing in Individual Subjects

At investigator discretion, for subjects' safety, dosing with any or all double-blinded investigational product/s, may be stopped in an individual subject – either temporarily or permanently. In such cases, any open TEAEs (treatment emergent adverse events) must be followed to resolution or until such time that the event is viewed to have stabilized – refer to [Section 8](#) for details.

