5.1. Allocation to Treatment

The investigator's knowledge of the treatment should not influence the decision to enroll a particular subject or affect the order in which subjects are enrolled.

Each eligible subject will receive six treatments at six different test fields in a random order. There will be no subdivision into treatment groups.

The test fields will be numbered 1-6. As far as possible the following procedure for numbering will be followed: The numbering should begin with the uppermost or most proximal site on the left from the investigator's view. Fields along the same line should be numbered from left to right. If more than one plaque is included, numbers for the fields on the next plaque will be assigned likewise starting with the next free number. The exact location of each test field in relation to the outline of the plaque(s) will be traced on a transparent plastic sheet which will be kept with the subject's source data. The location of the test fields will be documented in the Case Report Form (CRF) as:

Upper/lower left/right arm,

Upper/lower left/right leg,

Front/back trunk.

At screening, a subject will be assigned a subject number. Once the subject meets all eligibility criteria, the subject will be randomized into the study according to the randomization schedule, which is generated through the Pfizer randomization system. Randomization will be performed by permutation of the six treatments. At randomization, each eligible subject will be assigned a randomization number, which corresponds to a random permutation of six treatments. The treatment listed first in the respective treatment sequence will be assigned to test field number 1, the second treatment to test field number 2, etc.

Subjects are blinded to the treatment sequence throughout the study. Investigators will be blinded to the treatment sequence except exceptional circumstances described in [Section 5.2](#). Limited site staff who administer the treatments will be unblinded.

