If the subject withdraws from the study and also withdraws consent for disclosure of future information, no further evaluations should be performed and no additional data should be collected. The sponsor may retain and continue to use any data collected before such withdrawal of consent.

Subjects who withdraw from the study for ***non-safety reasons*** may be replaced at the discretion of the sponsor. Up to 5 subjects may be replaced.

Withdrawal of consent:

Subjects who request to discontinue receipt of study treatment will remain in the study and must continue to be followed for protocol-specified follow-up procedures. The only exception to this is when a subject specifically withdraws consent for any further contact with him or her or persons previously authorized by the subject to provide this information. Subjects should notify the investigator in writing of the decision to withdraw consent from future follow-up, whenever possible. The withdrawal of consent should be explained in detail in the medical records by the investigator, as to whether the withdrawal is only from further receipt of investigational product or also from study procedures and/or posttreatment study follow-up, and entered on the appropriate CRF page. In the event that vital status (whether the subject is alive or dead) is being measured, publicly available information should be used to determine vital status only as appropriately directed in accordance with local law.

Lost to follow-up:

All reasonable efforts must be made to locate subjects to determine and report their ongoing status. This includes follow-up with persons authorized by the subject as noted above. All attempts should be documented in the subject's medical records. If it is determined that the subject has died, the site will use locally permissible methods to obtain the date and cause of death. If, after all attempts, the subject remains lost to follow-up, then the last-known-alive date as determined by the investigator should be reported and documented in the subject's medical records.

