9.2.1. Analysis of the Primary Endpoint

The primary endpoint for this study is the change relative to baseline in psoriatic skin infiltrate thickness/EPB at Day 19 [REDACTED] for PF-06763809 in comparison to vehicle. The efficacy assessment of PF-06763809 will be performed for the change from baseline in log of the psoriatic skin infiltrate thickness/EPB on Day 19 using a longitudinal analysis of covariance model, with treatment, visit, treatment by visit interaction as main effects and the log of the psoriatic skin infiltrate thickness/EPB at baseline as covariate. The CS@UN covariance structure will be assumed to adequately model the two within-subject factors (treatment, visit), where the compound symmetric (CS) correlation is for repeated measures from different treatments within each visit and the unstructured (UN) correlation is for longitudinal measures from different visits. If there are convergence issues, alternative covariance structure will be examined and adopted. The point estimate and 95% confidence interval (CI) for the difference in log transformed means at Day 19 visit between treatment groups will be constructed using least square means and appropriate standard errors. The assessment of the primary endpoint will be performed at a two-sided significance level of 0.05. In this primary analysis, the missing data will be assumed as missing at random and no imputation will be made for missing data.

In addition, a landmark analysis of covariance (ANCOVA) model analysis of the primary endpoint at Day 19 will be performed to examine the robustness of the conclusion drawn from the primary longitudinal analyses. The landmark ANCOVA model will include treatment as the main effect, log-transformed psoriatic skin infiltrate thickness/EPB at

baseline as covariate and a random subject effect to account for correlation among repeated measures from different treatments for each subject. Missing assessments of psoriatic skin infiltrate thickness/EPB at Day 19 will be imputed using the last observation carried forward (LOCF) procedure. In case of treatment discontinuation the last assessment prior to treatment discontinuation will be imputed for the following planned assessment of psoriatic skin infiltrate thickness/EPB.

CCI

CCI

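### Does the LOCF sentence on treatment discontinuation leave the landmark analysis undefined when one test field stops early?

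*SAP*

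**What the plan says.** Protocol 9.2.1 and SAP 8.1 define two analyses of Day 19 EPB. The primary one is a longitudinal model that treats missing data as missing at random and imputes nothing. The second is a landmark ANCOVA at Day 19, added to check robustness. Only the second uses LOCF.

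Its imputation rule has two sentences, in near-identical form in SAP 7 and protocol 9.2.1. The protocol's first sentence reads: "Missing assessments of psoriatic skin infiltrate thickness/EPB at Day 19 will be imputed using the last observation carried forward (LOCF) procedure". The next, in SAP 7, reads: "In case of treatment discontinuation the last assessment prior to treatment discontinuation will be imputed for the following planned assessment".

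Three other places bear on it:

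- Protocol 3.2: dosing with any or all products "may be stopped in an individual subject – either temporarily or permanently".
- Protocol 5.1: "Each eligible subject will receive six treatments at six different test fields in a random order".
- Protocol 6.4: "Subjects who request to discontinue receipt of study treatment will remain in the study and must continue to be followed".

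The endpoint is "Change relative to baseline at Day 19 in psoriatic skin infiltrate thickness/EPB" (SAP 6.1.1).

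**The concern.** Read alone, the second sentence does not contain the word missing. Taken literally, it tells the programmer to put the last pre-stop EPB into the next planned assessment even if that assessment was made. It also leaves the unit open. Protocol 5.1 uses treatment for what is applied to one field, while protocol 6.4 speaks of subjects who give up study treatment as a whole. Protocol 3.2 adds temporary stops, which the sentence does not mention.

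The situation is not far-fetched. The toxicology summary (protocol 1.2.3) reports "vehicle-related mild to moderate skin irritation by the topical route of administration", and skin reactions at the application sites are watched closely. A subject could have one field stopped, stay in the study and attend Day 19. Two programmers could then build different landmark datasets from the same data. A difference between the landmark and the primary result would be harder to interpret, because it might reflect the imputation reading and not the robustness of the finding.

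**Working it through.** The plan states no figure for this rule, and the table behind the sample size is blacked out, so there is nothing to reproduce. The check compares the readings, then gives a scale.

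**1. Where the readings differ.** For one test field:

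| Situation | Imputation only if Day 19 is missing | Literal overwriting |
|---|---|---|
| Dosing not stopped, Day 19 measured | measured value | measured value |
| Dosing stopped, Day 19 measured | measured value | last pre-stop value |
| Dosing stopped, no EPB afterwards | last pre-stop value | last pre-stop value |
| Dosing stopped, EPB measured after the stop, Day 19 missing | last pre-stop value, by the second sentence | last pre-stop value |

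Only the second row separates the two readings. In the fourth row the general LOCF sentence alone would carry the post-stop value. The more specific second sentence selects the pre-stop one.

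**2. Missing values only?** The SAP section is about missing values, the sentence before concerns missing assessments, and the protocol's version names missing Day 19 assessments. A measured value is not missing. The second sentence still has a job under this reading: it says which value to carry.

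**3. Unit.** The landmark model (SAP 8.1) has one record per treatment within subject, and protocol 5.1 ties each treatment to one field. A field still being dosed has no assessment prior to discontinuation to carry. Replacing all six fields after a single-field stop is therefore a strained reading.

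**4. Pause.** Protocol 5.5 has a subject who misses a day return at the next occasion, and treats discontinuation as a separate, discretionary step after more than one missed dose. A pause is not naturally a discontinuation, although no definition is given.

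**5. Scale if a measured value were overwritten.** Inputs: n = 15 completers (protocol 9.1); calcipotriol benchmark of 38% with SD 0.435 (protocol 1.2.4). Assumption: d, the log-EPB difference between the last pre-stop and the Day 19 value, lies between half and all of the benchmark. Covariate adjustment is ignored and the data are taken as balanced.

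- Benchmark on the log scale: -ln(1 - 0.38) = 0.478; half is 0.239.
- Shift in the active-vehicle contrast for one stopped active field, d/n: 0.239/15 = 0.016 to 0.478/15 = 0.032.
- Standard error if the SD is per field: 0.435 × √(2/15) = 0.159. If it is the SD of the paired difference: 0.435/√15 = 0.112.
- Ratio to the standard error: smallest 0.0159/0.159 = 0.10; largest 0.0319/0.112 = 0.28.
- As a percentage, the largest shift moves a 38% reduction to 1 - 0.62 × exp(0.0319) = 36.0% or 1 - 0.62 × exp(-0.0319) = 39.9%.
- If the five permitted replacements also stay in the FAS (n = 20): 0.239/20 = 0.012 to 0.478/20 = 0.024.
- The shift grows with the number of stopped fields of the same treatment. Three at the full d give 3 × 0.478/15 = 0.096, which is 0.60 (SE 0.159) to 0.85 (SE 0.112) standard errors.

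The shift is zero if no field stops, if d = 0, or if the measured value is kept. It cancels if an active and a vehicle field stop together with equal d.

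**The case for a change.** The best case for a change is that if no EPB follows the stop, ordinary LOCF already carries the last pre-stop value and the second sentence adds nothing. It must have been written for cases where a later EPB exists, and those are the cases where it is least clear. The per-protocol analysis does not settle them. SAP 5.2 excludes subjects with major deviations or early study discontinuation, and a single-field stop in a subject who stays is by its wording neither. One added sentence before unblinding would cost almost nothing.

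Part of this stands. The text is not explicit on any of the three points, and the situations are possible under the protocol. But the sentence also has work to do without overwriting data, as the fourth row of the table shows. Keeping post-stop values and setting them aside are both defensible for a robustness check, so the documents show no wrong method to replace. Whether a stopped field is measured at Day 19 at all may also be stated in blacked-out text: the EPB rows of the schedule are not visible, nor are the assessment sections after protocol 7.1.5 or the text after 9.2.1. SAP 5.7 has all deviations reviewed before database closure and classified before unblinding. That review does not write the imputation rule, but it may bring irregular cases to light while the team is blinded.

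**Conclusion.** This is a gap in wording that analysts fill sensibly: apply the rule per test field, only where Day 19 EPB was not measured, and carry the last value before permanent discontinuation of that field. The context favours each part of that reading.

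No decision depends on it. SAP 4.2 rests the primary assessment on the longitudinal model, which makes no imputation, so its estimate, its test and the sample size are untouched. The landmark analysis is a robustness check, and SAP 7 requires LOCF displays to be labelled as such.

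The effect on the landmark result cannot be determined, because the documents give neither a stop rate nor a post-stop course of EPB. The 0.10 to 0.28 standard errors for one stopped active field rest on an assumed d and on the less natural overwriting reading. Several stopped fields of one treatment would give more. Under the natural reading, a measured Day 19 value stays and nothing shifts. A sponsor who wishes to spell the reading out may do so, but the plan does not need it.
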